#### 666 **5.4 Data and Safety Monitoring Board**

667 An independent Data and Safety Monitoring Board will approve the protocol prior to its initiation  
668 and will be informed of all serious adverse events and any unanticipated adverse device events that  
669 occur during the study.  
670

#### 671 **5.5 Risks and Discomforts**

672 The FDA has determined that this protocol will require an Investigational Device Exemption (IDE).  
673 Adequate safeguards are in place to ensure that exposure to the risks associated with study  
674 participation are minimized to the extent possible.  
675

676 The planned study also includes a Subcutaneous Insulin Infusion Test on the morning following the  
677 overnight admission during which slightly increased insulin doses will be used to achieve gradually  
678 falling blood glucose levels while serial blood samples are obtained for measurement of various  
679 counter-regulatory hormones. Glucose levels will be checked using a home glucose meter every 15  
680 minutes until the glucose level of  $\leq 100$  mg/dl is reached, after which glucose will be measured  
681 every 5 minutes and the test stopped once the glucose level reaches  $\leq 60$  mg/dl. Thereafter, the basal  
682 insulin rate will be restored, children will be treated with IV glucose to restore blood glucose and  
683 then eat breakfast prior to discharge. A significant proportion of patients will not report symptoms  
684 of hypoglycemia at this glucose level and progression to severe hypoglycemia is extremely unlikely  
685 with the careful monitoring that is planned. Given the careful safeguards in place, we would argue  
686 that the Subcutaneous Insulin Infusion Test poses no more than a minor increase over minimal risk  
687 for these children.  
688

689 Further, there are a number of potential benefits that could accrue to participants. First, all  
690 participants will be able to use the Guardian RT for approximately 6 days prior to the CRC  
691 admission. This could reveal previously unrecognized glucose trends, particularly during  
692 postprandial periods and during sleep, thus enhancing diabetes management. Second, the study  
693 could reveal whether an individual patient mounts a counter-regulatory hormone response to mild  
694 hypoglycemia and/or slowly falling glucose levels. Such information could help to gauge the degree  
695 to which avoidance of hypoglycemia should be prioritized in that patient's diabetes management.  
696 Finally, the study will yield information about glycemic sensitivity to modest changes in basal  
697 insulin infusion rates that could inform subsequent self-management decision making by children  
698 and parents. Thus, the planned study offers the prospect of several meaningful direct benefits to  
699 participants as well as contributing valuable knowledge about counter-regulatory hormone action  
700 during mild hypoglycemia in two age groups of children with diabetes.  
701

702 Our previously completed DirecNet protocol entitled "The Accuracy of Continuous Glucose  
703 Monitors in Children with Type 1 Diabetes" posed similar risks to study participants and affords the  
704 best perspective for evaluating the risks and benefits associated with the planned study. In that prior  
705 study, children between the ages of 1 and  $<18$  years were admitted to the Clinical Research Center  
706 at a participating site for an approximate 26 hour hospitalization. Children wore two different kinds  
707 of continuous glucose monitors throughout those admissions (Cygnus GlucoWatch 2 Biographer  
708 and Medtronic Minimed CGMS) while serial blood samples were drawn for comparison of glucose

709 values obtained by those devices with central laboratory results. Blood samples were drawn through  
710 an indwelling heparin lock every 60 minutes during waking hours and every 30 minutes during  
711 sleep. Children also underwent an IV insulin challenge ( $\geq 7$  years old only) and a meal challenge (all  
712 children) so that sensor accuracy could be evaluated during periods of rapidly falling and rapidly  
713 rising glucose levels, respectively. Carefully calculated limits ensured that the volume of blood  
714 samples drawn was safe based on each child's weight. There were no significant adverse events  
715 during this study. Skin reactions were associated with use of the GlucoWatch in a significant  
716 proportion of the children enrolled in that study, but that device will not be used in the planned  
717 study.

718  
719 As in the previously completed study, the volume of blood samples to be collected will not exceed  
720 5% of the subject's total blood volume.

721  
722 In comparison to this previously completed study, the planned protocol includes a shorter CRC  
723 admission (18 vs. 26 hours).

724  
725 **5.5.1 Hypoglycemia**  
726 Subjects may develop hypoglycemia. Severe uncontrolled hypoglycemia may be associated with  
727 profuse diaphoresis, shock, tachycardia, and seizures. Hyperglycemia is usually acutely benign, but  
728 may be associated with thirst, glycosuria, ketoacidosis, and hyperosmolar coma. The risk of these  
729 complications is an inherent risk of having diabetes.

730  
731 The purpose of this study is to examine the effect of age on hormonal responses to mild  
732 hypoglycemia (i.e. the study will be stopped when the plasma glucose level falls below 60 mg/dl).  
733 This plasma glucose level was selected because it is extremely unlikely to cause any major  
734 symptoms and because blood glucose levels considerably lower than 60 mg/dl are commonly  
735 experienced by children and adolescents with T1DM. In our recent DirecNet study(23),  
736 approximately 25% of children and adolescents had plasma glucose levels below 60 mg/dl during a  
737 typical night and this rose to approximately 50% of subjects when there was antecedent exercise in  
738 the late afternoon. Moreover, the frequency of mild as well as severe hypoglycemia is substantially  
739 higher in pre-school children than in children and adolescents. The insulin infusion doses have been  
740 designed to cause a gradual reduction in plasma glucose and the study will be performed in a  
741 controlled environment with a physician available. Plasma glucose levels will be measured every 5  
742 minutes at the bedside when the plasma glucose level falls below 100 mg/dl. Once the glucose  
743 concentration reaches  $< 60$  mg/dl, hormone samples will be obtained and plasma glucose levels will  
744 be acutely raised by intravenous administration of glucose that will be available at the bedside. The  
745 study will also be terminated early if any of the children become very uncomfortable due to  
746 symptoms of hypoglycemia (e.g., sweaty, shaky, palpitations) at plasma glucose levels that are  $> 60$   
747 mg/dl. Such close monitoring of plasma glucose levels ensures that there will be virtually no risk  
748 that the plasma glucose concentration will fall into a dangerous zone that might result in an  
749 alteration in level of consciousness or other sign or symptom of more severe hypoglycemia.

750  
751 Based on the fact that (1) children with diabetes experience mild hypoglycemia frequently as a  
752 consequence of the disease and its management, (2) the study induces a gradual drop in blood  
753 glucose under careful medical monitoring, (3) a conservative glucose nadir of 60mg/dl will be  
754 carefully enforced with glucose determinations being made every 5-minutes, and (4) rapid reversal  
755 of hypoglycemia can be achieved it is the assessment of the investigators that this protocol falls  
756 under DHHS 46.405 which is a minor increase over minimal risk. In addition, it is the belief of the  
757 investigators that this study also presents prospect of direct benefit to the subjects and general  
758 benefit to others with diabetes as described in Section 6.1.

759

760 **5.5.2 Guardian-RT**

761 There is a low risk for developing a local skin infection at the site of the sensor needle placement.  
762 Itchiness, redness, bleeding, and bruising at the insertion site may occur. The FDA approval of the  
763 Guardian RT is for a 3-day wearing period for each sensor. Nonetheless, a longer wearing period  
764 should be safe, effective, and more acceptable to patients. With a longer wearing period, the risk of  
765 skin reactions may increase.

766

767 **5.5.3 HypoMon**

768 There are no known risks associated with use of the HypoMon.

769

770 **5.5.4 Fingerstick Blood Glucose Measurements**

771 Fingersticks may produce pain and/or ecchymosis at the site.

772

773 **5.5.5 IV Risks**

774 A hollow needle/plastic tube will be placed in the arm for taking blood samples or giving fluids  
775 during the CRC admission. This will be left in for approximately 18 hours. When the needle goes  
776 into a vein, it can cause pain. A special cream (Elamax or EMLA®) may be used to numb the area  
777 where the needle will be inserted. The most common risks related to putting the numbing cream on  
778 the skin are redness, blanching (temporary whiteness of the skin area), swelling, and itching. There  
779 will be the minor discomfort of having the needle/plastic tube taped to the arm. In about one in 10  
780 cases a small amount of bleeding under the skin will produce a bruise. The risk of a blood clot  
781 forming in the vein is about one in 100, while the risk of infection or significant blood loss is one in  
782 1000.

783

784 **5.5.6 Blood Volume Requirements**

785 At the time of CRC admission the maximum number of blood draws that can be performed based  
786 on a subject's weight will be determined so that the maximum blood volume in the blood draws will  
787 not exceed 5% of the subject's blood volume (calculated by multiplying the subject's weight in  
788 kilograms by 70 [70cc / kg blood volume] and then multiplying by .05). The maximum number of  
789 blood draws is then determined by dividing this maximum blood volume by the amount of blood in  
790 each blood draw at the center.

791

792 The table below shows the blood volumes for each procedure at the "reinfusion" and "discard"  
793 centers. For blood draws for evaluation of the accuracy of the Guardian RT a blood volume of 1.3  
794 ml per blood draw at the "discard" centers and 0.3 ml per blood draw at the "reinfusion" centers is  
795 assumed. At the "discard" centers, the maximum number of blood draws per subject will be  
796 adjusted if the blood draw amount exceeds 1.3 ml.

797

798 **Table 5.1 Blood Volume Requirements for Procedures According to Type of Blood Draw**

Procedure	# of blood draws	Type of Blood Draw Employed at the Clinical Center	
		"Reinfusion" (Volume to be drawn)	"Discard" (Volume to be drawn)
A. Subcutaneous Insulin Infusion Test	6	44.5 (0.3 ml per blood draw)	60.5 (1.3 ml per blood draw)
B. Half-Hourly measurements for 12 hrs	24	7.2	31.2
C. Quality control sample	1	0.3	1.3
D. Meal-induced hyperglycemia test	8	2.4	10.4

799

800 The tables below indicate the procedures to be done based on the age and/or weight of the subjects.

801  
802 **Table 5.2: Procedures to Be Done / Blood Volume Required According to Weight of Subject**

803  
804 **A. “Reinfusion” Centers**

	Procedure (see description in Table 5.1 for each ‘letter’)				
Subject Weight	A	B	C	D	Total Blood Volume
12.8 to <14.9 kg	44.5	--	0.3	--	44.8
14.9 to 15.5 kg	44.5	7.2	0.3	--	52.0
>15.6 kg	44.5	7.2	0.3	2.4	54.4

805

806

807 **B. “Discard” Centers**

	Procedure (see description in Table 5.1 for each ‘letter’)				
Subject Weight	A	B	C	D	Total Blood Volume
17.4 to <26.3 kg	60.5	--	0.3	-	60.8
26.3 to 29.2 kg	60.5	31.2	0.3	-	92.0
>29.3 kg	60.5	31.2	0.3	10.4	102.4

808

\* based on adjusted schedule of every 30 min overnight (9PM – 6AM) and hourly at other times

809

810 The study may include other risks that are unknown at this time.

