  - 566 ○ If the sensor is not functioning at the time of the admission, a new sensor will be  
567 inserted.
- 568 • For subjects of sufficient size, a second Guardian-RT will be inserted. The time of  
569 placement and the placement site of each sensor will be recorded.  
570

571  
572 For subjects of sufficient weight to accommodate the blood volume requirements, reference glucose  
573 measurements will be made every 30 minutes during the CRC admission for evaluation of the  
574 accuracy of the Guardian-RT. The blood draws will be timed to be on the half-hour.  
575

576 During the insulin-induced hypoglycemia test, blood glucose measurements will be made as  
577 described in section 3.3.  
578

579 For subjects of appropriate weight to accommodate the volume of blood required for testing, the  
580 Guardian RT will be assessed following a physiologic rise in blood glucose after dinner.  
581

582 Before starting the post-meal glucose measurements, a blood glucose level will be obtained using  
583 the study HGM. The subject's usual meal dose (the dose for the carbohydrates to be  
584 consumed) will be given, and a correction dose will be given if needed. Reference glucose levels  
585 will be obtained at baseline (when the subject finishes the meal) and every 15 minutes for 120  
586 minutes.  
587

588 **4.2.1 Volume of Blood Draws**

589 Each blood draw will require a blood volume of approximately 1.3 ml per blood draw at the  
590 "discard" centers and 0.3 ml per blood draw at the "reinfusion" centers. At the "discard" centers,  
591 the maximum number of blood draws based on the subject's weight will be calculated at the time of  
592 admission so that the maximum blood volume drawn will not exceed 5% (at reinfusion centers, the  
593 maximum blood volume drawn will not approach 5%). Section 5.5.6 provides further details on the  
594 blood volume requirements.  
595

596 **4.2.2 Quality Control Specimens**

597 Approximately 5% of the reference blood samples collected for evaluation of the Guardian-RT will  
598 be collected in duplicate to send to the central lab for quality control purposes.  
599

600 **4.2.3 Sensor Considerations during Inpatient CRC Admission**

601 **4.2.3.1 Sensor Calibrations**

602 If a calibration of the Guardian-RT is required during the admission, it will be performed by  
603 study/CRC personnel using a fingerstick sample.

604

605 **4.2.3.2 Sensor Failure**

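### The 5-minute glucose checks in the risk argument are not required by the test procedure, and Tables 5.1 and 5.2 disagree on the discard-center quality-control volume and the infusion-test draw count

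*Protocol*

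**What the plan says.** **Check interval.** Sections 1.3 and 3.3.1 set 15-minute venous meter checks until glucose is down to 100 mg/dL, then checks 5 to 10 minutes apart depending on how fast it falls. Sections 5.5 and 5.5.1 give the later interval as 5 minutes. Section 5.5.1 lists it among four grounds for placing the study under 46.405.

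**Blood volumes.** Section 5.5.6 caps blood drawn at 5% of 70 ml/kg.
- In Table 5.1, "C. Quality control sample" is one draw: 0.3 ml at reinfusion centers, 1.3 ml at discard centers. Table 5.2B enters 0.3 ml for it in all three weight rows.
- Row A (the infusion test) lists 6 draws. It prints 44.5 ml at 0.3 ml per draw for reinfusion centers and "60.5 (1.3 ml per blood draw" for discard centers.
- The admission rule says that the maximum number of "blood draws is then determined by dividing this maximum blood volume by the amount of blood in" each draw.

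**Accuracy draws.** Section 4.2 says that reference "measurements will be made every 30 minutes during the CRC admission for evaluation of the" sensor's accuracy, and 1.3 says much the same. Table 5.1 budgets "B. Half-Hourly measurements for 12 hrs" as 24 draws. A footnote to Table 5.2 is "based on adjusted schedule of every 30 min overnight", with hourly draws at other times.

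**The concern.** The 5-minute interval is offered as a safeguard for children as young as 3 years. A site that checks every 10 minutes complies with 3.3.1 but does not provide what the risk section describes.

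The volume tables set who may enter and what is done to them. The 17.4 kg minimum at discard centers is an eligibility criterion (2.2.1), and 26.3 kg is the threshold for half-hourly sampling there (1.3). The protocol says the 5% cap will not be exceeded, and the cut-offs leave almost no slack, so a wrong cell or a wrong draw count bears directly on that statement.

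**Working it through.** **1. Check interval, side by side.** Sections 1.3 and 3.3.1: 5 to 10 minutes. Sections 5.5 and 5.5.1: 5 minutes. The second is stricter and nothing in the procedure sections enforces it.

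**2. Reproducing the printed cut-offs.** Cap = weight × 70 × 0.05 = 3.5 ml/kg. Minimum weight = total volume / 3.5, rounded up to 0.1 kg.
- Reinfusion: 44.8/3.5 = 12.80; 52.0/3.5 = 14.86 → 14.9; 54.4/3.5 = 15.54 → 15.6 kg.
- Discard, quality-control (QC) sample 0.3 ml: 60.8/3.5 = 17.37 → 17.4; 92.0/3.5 = 26.29 → 26.3; 102.4/3.5 = 29.26 → 29.3 kg.

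All six reproduce.

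**3. Discard centers with the Table 5.1 value of 1.3 ml.** Each total rises by 1.0 ml.

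| Printed cut-off | Cap there | Total | Over cap | Share of blood volume | Cut-off needed |
|---|---|---|---|---|---|
| 17.4 kg | 60.90 ml | 61.8 ml | 0.90 ml | 5.07% | 17.66 → 17.7 kg |
| 26.3 kg | 92.05 ml | 93.0 ml | 0.95 ml | 5.05% | 26.57 → 26.6 kg |
| 29.3 kg | 102.55 ml | 103.4 ml | 0.85 ml | 5.04% | 29.54 → 29.6 kg |

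**4. Row A.** The per-draw volumes differ by 1.3 − 0.3 = 1.0 ml, so 6 draws would separate the center types by 6.0 ml. The printed gap is 60.5 − 44.5 = 16.0 ml. With 6 draws, the blood left for hormone samples would be 44.5 − 6 × 0.3 = 42.7 ml at one center type and 60.5 − 6 × 1.3 = 52.7 ml at the other, for the same samples. With 16 draws both remainders are 39.7 ml (44.5 − 4.8 and 60.5 − 20.8). The 16 is back-solved, not stated.

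**5. Slack at the cut-offs.** One draw more than budgeted passes the cap at every one (discard totals with QC 0.3 ml):
- Reinfusion (+0.3 ml): 45.1 against 44.8 ml at 12.8 kg; 52.3 against 52.15 at 14.9 kg; 54.7 against 54.6 at 15.6 kg.
- Discard (+1.3 ml): 62.1 against 60.9 ml at 17.4 kg; 93.3 against 92.05 at 26.3 kg; 103.7 against 102.55 at 29.3 kg.

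**6. Admission rule.**
- As worded, 17.4 kg at a discard center: 60.9/1.3 = 46.8, so 46 draws. Row A leaves 60.9 − 60.5 = 0.4 ml, less than one 1.3 ml draw.
- As worded, 26.3 kg: 92.05/1.3 = 70.8, so 70 draws.
- After subtracting row A and 0.3 ml QC, 26.3 kg: (92.05 − 60.5 − 0.3)/1.3 = 24.04, so 24, which is row B.
- Likewise 29.3 kg: (102.55 − 60.8)/1.3 = 32.1, so 32 = 24 + 8, which is rows B and D.

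The rule with subtraction gives back the schedule in Table 5.2B; the printed rule does not.

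**7. Accuracy schedule.** The footnote's 9 overnight hours give 18 half-hourly draws. Six hourly draws bring that to 24, compatible with row B. Half-hourly draws throughout an 18-hour admission would be more than 24.

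**The case against.** Much of the case for leaving things alone is fair.

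- **QC volume.** Section 4.2.2 says these samples will "be collected in duplicate to send to the central lab for quality control purposes". A duplicate taken with another draw needs no second dead-space discard, so 0.3 ml is plausible and the Table 5.1 cell may be the only slip. A reader might infer that children will be bled beyond 5%. The documents do not show that: there is no excess at 0.3 ml, and at 1.3 ml it is under 1 ml and confined to children within about 0.3 kg above a cut-off.
- **Row A.** The 6 matches the six sampling time points in 3.3.2, and no total or cut-off uses the count. A reader might take 16 as the true budget and work out how long a test it covers. That would rest on an inferred count and on treating each meter check as one budgeted draw, so no duration claim is made here. The mismatch between 6 and the volumes stands.
- **Admission rule.** A reader might infer that 70 draws are permitted. Table 5.2 fixes which procedures are done at each weight with row A included, and 5.5.6 states the 5% limit outright, so the defect is in the formula's wording.
- **Check interval.** Five minutes lies within 5 to 10, so a site can satisfy both texts, and the interval is one of four grounds. The conflict does not overturn the 46.405 classification. It does leave a stated safeguard optional.
- **Accuracy schedule.** A reader might infer that half-hourly draws through the whole stay would break the cap. The 24-draw budget and the footnote indicate that this is not intended.
- **Section 4.2.1.** The remark that at reinfusion centers the "maximum blood volume drawn will not approach 5"% might look false against Table 5.2A totals of 4.98 to 5.00% at the cut-offs. It directly follows the accuracy-draw volumes, and for those it holds: (7.2 + 0.3 + 2.4)/(15.6 × 70) = 9.9/1092 = 0.9%. It is not an error.

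**Conclusion.** The inconsistencies are real and rest on the protocol's own figures. Two should be fixed: the check interval, because the safeguard cited in the risk argument is not required by the procedure; and the discard-center QC volume, because an eligibility weight and the 5% limit depend on it. The second is worth 1.0 ml, or 0.3 kg on each discard cut-off, and only if 1.3 ml is the intended value; the documents do not settle that. The row A count, the admission formula and the half-hourly wording are minor. Row A gains weight if 5-minute checks become mandatory, because one unbudgeted draw passes the cap just above every cut-off. Nothing here affects the statistical design or the analysis.

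**What to change.** 1. **Check interval.** Require 5-minute venous checks in 1.3 and 3.3.1, or restate the interval and the risk argument in 5.5 and 5.5.1. The first option costs more venous draws. Moving late checks to fingersticks to save blood is not advised: it changes the specimen that triggers the hormone samples and the endpoint, and adds a painful stimulus during the hormone test.
2. **QC volume.** State one value for discard centers. If 0.3 ml, correct only the Table 5.1 cell. If 1.3 ml, change the Table 5.2B totals to 61.8, 93.0 and 103.4 ml and set the cut-offs to 17.7, 26.6 and 29.6 kg wherever they appear in 1.3, 2.2.1 and Table 5.2B. That would exclude a few of the lightest discard-center children.
3. **Row A.** Give the true number of draws, including meter checks, and show the hormone volume separately. If 5-minute checks need more draws than budgeted, re-derive row A and all cut-offs.
4. **Admission rule in 5.5.6.** Maximum accuracy draws = (3.5 ml/kg × weight − row A − QC) / volume per draw.
5. **Accuracy schedule.** Align the half-hourly wording in 1.3 and 4.2 with the Table 5.2 footnote.

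All of this is a table and wording amendment.

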**CHAPTER 6**  
**MISCELLANEOUS CONSIDERATIONS**

811  
812  
813  
814  
815  
816  
817  
818  
819  
820  
821  
822  
823  
824  
825  
826  
827  
828  
829  
830  
831  
832  
833  
834  
835  
836  
837  
838  
839  
840  
841  
842  
843  
844  
845  
846  
847  
848  
849  
850  
851  
852  
853  
854  
855  
856  
857  
858  
859  
860

**6.1 Benefits**

It is possible that subjects will not directly benefit from being a part of this study. However, it is also possible that the blood sugar and hormone information will be useful for subjects' diabetes management. Specifically, the study will offer participants the benefit of determining for each individual child the glucose level that triggers symptoms and the different types of symptoms and, conversely, how their child appears and what symptoms they have when the blood glucose level falls below 60 mg/dl. This information is especially valuable in young children, who are not developmentally able to relate to their care givers how they feel. Parents could use this information to help them with the daily management of these children's diabetes at home and thus prevent hypoglycemia and its neurologic and possibly developmental sequelae. It is beneficial for individuals to learn their idiosyncratic responses to falling glucose levels and for their physicians to identify patients who fail to mount a counter regulatory hormone response to low or falling glucose levels. Glycemic targets, correction doses, etc. might be modified accordingly in an effort to prevent hypoglycemia in such patients.

Results of this study will also provide important new knowledge that will be generalizable to all children with type 1 diabetes regarding defects in counter-regulatory hormone responses to hypoglycemia that make children in general and young children in particular vulnerable to hypoglycemia.

